The antidepressive effect of low frequency rTMS as addon to ECT. A pilot study

The original dated 13.04.2015 written in Danish
Translated to English 11.12.20 (the submitted form)

NCT02123485

Introduction

rTMS (repetitive transcranial magnetic stimulation) is a potential new

noninvasive antidepressant method, which implies non-convulsive focal stimulation of the brain through a time varying magnetic field. rTMS is based on the principle of electromagnetism. An electromagnetic coil placed on the scalp produces an oscillating magnetic field that penetrates the scalp and skull unattenuated and gives rise to a current in the adjacent parts of the cerebral cortex as well as functionally connected centers of the brain. Previous research indicates that the antidepressant effect of rTMS is associated with specific stimulation of the dorsolateral prefrontal cortex. The stimulus frequency has been shown to play a key role in the mechanisms of action of rTMS. Preclinical studies have revealed that low frequency rTMS is associated with long-term inhibition of neuronal activity (long-term depression), while high frequency stimulation is followed by prolonged activation (long-term potentiation). To some extent, this differential effect of the two types of frequencies are reflected in human studies.

The majority of clinically controlled studies on the antidepressant efficacy of rTMS have used high frequency stimulation of left prefrontal cortex supporting the evidence of the antidepressant efficacy of this treatment model, which has been approved by the FDA in USA and later in the EU for the treatment of depression. Fewer studies have used right prefrontal low frequency rTMS, though this model of stimulation obviously has fewer side effects, such as local discomfort and a lower risk of releasing epileptic seizures, than high frequency stimulation. Both stimulus models have been shown to have a statistically and clinically significant antidepressant effect of equal magnitude as add-on to other antidepressant treatments including ECT.

ECT is used in approximately 5% of all psychiatric patients in Denmark with slightly increasing frequency of 11% since 1999. ECT acts through epileptic seizures and have a documented anti-kindling effect involving limbic and paralimbic structures. This kindling repressing effect is probably of significance for the mechanism of ECT. rTMS does not work by inducing seizures, but like ECT low frequency rTMS has been shown to inhibit amygdala-kindled seizures in animal studies. Therefore, theoretically it is possible that low frequency rTMS can amplify the antidepressant effect of ECT.

The present study will be carried out to investigate in which degree right prefrontal low frequency rTMS administered as add-on may accelerate the

antidepressant effect of ECT and thus minimize the side-effects of this treatment.

Material and methods

Design

The present study will be carried out as a randomized, clinically controlled, double blind investigation comparing conventional ECT + sham-stimulation with ECT + right prefrontal low frequency rTMS. Previous research concerning the antidepressant effect of ECT versus rTMS has found remission rates on ECT between 50 and 60%. On the basis of these figures and the outcome of previous RCT studies on the antidepressant effect of low frequency rTMS compared to placebo the difference in the incidence of remission was expected to be 20-30%. A rate difference of 20% would require 81 patients, while a rate difference of 30% would require 31 patients in each group to have 80% power in a 2-sided test at a 5% significance level.

Randomization

The patients are randomly allocated to ECT + rTMS or ECT + sham According to the principle of block randomization. Six blocks are created with 10 sealed opaque envelopes in each, half of them containing a treatment code for rTMS and the other half for ECT. The envelopes in each block are shuffled thoroughly and numbered from one to 10. To ensure allocation concealment, the patients were randomly allocated to treatment by an independent third part.

Ethics

The study meet the criteria of the Helsinki Declaration II. The patients' consent is based on written and oral information, and the regional ethics committee approved the project protocol.

Study Population

The study population covers inpatients with depression from the County of

Aarhus. The patients are admitted to the department for Depression and Anxiety, Aarhus University Hospital, Risskov, Denmark, and recruited primarily from the city of Aarhus with associated rural districts, a catchment area of approximately 300,000 inhabitants.

Inclusion criteria:

Age between 18 and 80 years and a total score on 17-item HAM-D (24) of 20 or higher and/or 9 or higher on the subscale.

All patients fulfill the ICD-10 criteria for moderate to severe depression and the Diagnostic and Statistical Manual of Mental Disorders-IV criteria for major depressive disorder. Unipolar as well as bipolar patients are included.

Exclusion criteria:

Patients with organic brain damage, personal or family history of epileptic seizures, metallic objects in the chest or brain, cardiac pacemakers, and somatic diseases associated with brain dysfunction were excluded from the study. Pregnancy, use of coercive measures, severe suicidal risk, severe agitation or delirium, and alcohol or drug dependence (ICD-10) constituted additional exclusion criteria.

General physical and neurological examination will be supplied by routine blood tests and an electrocardiogram.

Outcome measures

Primary effect measures: percentage of response and remission.

Secondary outcome measures: change in cognitive function.

Depression severity is evaluated using the Hamilton 17-item, the 6-item scale for depression (HAM-D6) and the Major Depression Inventory scale (MDI)

Response defined as a 50 % reduction in total HAM-D score and remission as a total HAM-D (17-item) score of 8 or lower.

Adverse effect is further assessed by a scale based on the Udvalg for Kliniske Undersøgelser (UKU: Committee for Clinical Investigations) side effect rating scale

Changes in the degree of depression and adverse effects will be assessed at baseline (before treatment) at weekly intervals within 24 hours after 3. 6. and 9. ECT. Additional HAM-D, MDI's and UKU ratings are carried out 4 weeks after termination of the treatment period. Trained clinicians carry out quantitative and diagnostic ratings.

The cognitive function. Patients will be assessed before each treatment course, within 48 hours and 4 weeks after last ECT. Global cognitive functioning is assessed with a short test battery comprising measures of attention and speed (Trail-Making Tests A and B, visual and verbal memory and learning (Rey Complex Figure Test, Logical Memory/ Wechsler Memory Scale Revised, and Executive Function as in Verbal Fluency semantically and phonologically.

Pharmacological Treatment

Concomitant antidepressant treatment is monitored continuously during the investigation. During the treatment period (from baseline until the end of week 3), psychopharmacological treatment is held constant. If possible, benzodiazepines will be tapered off 2 to 3 days before the first ECT. In case of severe anxiety, oxazepam will be used before 5 PM the day before treatment. If sleeping medication was needed, zolpidem or quetiapine will be preferred. Antiepileptic's prescribed as mood stabilizers are discontinued (lamotrigine dose was halved) before the first treatment. After termination of the treatment period, the patients continue any psychopharmacological medication with no restrictions.

rTMS treatment was carried out by a MagPro type R30 (MagVenture A/S, [name]) stimulator, which is certified by the EU for treatment of depression, using a water-cooled double blind, figure eight placebo spool (type Cool-B65 A/P Butterfly Coil).

The motor threshold will be determined by placing the center of the coil on a line connecting the vertex with the auditory meatus, stimulating the cortex to find the lowest intensity that produced a visual motor response in the tenar of the left hand. The treatment site over the right dorsolateral prefrontal cortex is then found by moving the coil 5 cm anterior to this point at a right angle to the line connecting the auditory meatus and the vertex.

The patients receive either placebo stimulation or two 180-second 1-Hz trains delivered at an intensity of 110% of motor threshold with a 180 seconds intertrain interval. This procedure is followed two times a week on ECT-free

days ie. on Tuesdays and Thursdays as ECT is delivered on Mondays, Wednesdays, and Fridays.

Blinding

The result of the randomization (active or sham rTMS) will be downloaded by an independent third part to a patient Key (USB memory stick) that will be sent to the treatment center and inserted in the MagPro stimulator.

The coil, which is identical on both sides, had a built-in position sensor used to ensure that the correct (active or sham) side of the coil faced towards the patient's head. If the coil position is wrong, the operator receive the display message a "Flip Coil" prompt on the MagPro screen. To ensure blinding of patients, electrodes from the MagPro will be used to stimulate the patient's skin in the coil area to mimic real rTMS.

Electroconvulsive Therapy

Thymatron (Fred Berninger Import OHG, Taufkirchen, Germany) (maximum dose of stimulation, 1008 milli coulombs) is used for ECT. Patients elected for this type of treatment received 9 ECTs on the average during the project period. The treatment is administered 3 times weekly with handheld electrodes according to the guidelines of the Danish Psychiatric Society .

Statistics

Treatment and placebo groups will be compared based on a t-test or chi-square test dependent on which was most suitable. The effect of treatment on HAMD₆, HAM-D₁₇ and MDI over time will be evaluated based on a last observation carried forward as well as quadratic linear mixed model. The effect of treatment on cognitive function over time will be evaluated based on a linear mixed model.

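### The 80% power claimed for 81 and 31 patients per group holds only near 58–60% control remission, and the 60 envelopes prepared give 35–39% power at 20 points and 69–80% at 30

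*Combined protocol and SAP*

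**What the plan says.** The sizing is in the Design section. It reports that earlier research "has found remission rates on ECT between 50 and 60" per cent, and that "the difference in the incidence of remission was expected to be 20-30" per cent. It then states: "A rate difference of 20% would require 81 patients, while a rate difference of 30% would require 31 patients in each group", for 80% power in a two-sided test at 5%. It does not say which control rate or formula produced the two sizes, which of the two differences the trial is sized for, or how many patients will be enrolled. No dropout allowance is given.

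The Randomization section holds the only number that implies a total: "Six blocks are created with 10 sealed opaque envelopes in each". The split within a block is even, with "half of them containing a treatment code for rTMS and the other half for ECT".

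Under Outcome measures the plan names "Primary effect measures: percentage of response and remission". Under Statistics it says "Treatment and placebo groups will be compared based on a t-test or chi-square test dependent on which was most suitable". The title reads "The antidepressive effect of low frequency rTMS as addon to ECT. A pilot study", but the text does not say what pilot status means for the size or for reading the result.

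**The concern.** A reader of the Design section takes away that the trial has 80% power for a 20–30 point gain in remission. Two features of the plan prevent that reading.

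First, the size needed for a given gain depends on the control rate, and the plan offers a range of control rates but only one size per gain. If the sizes belong to the favourable end of the range, the claim is untrue at the other end.

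Second, the plan prepares 60 allocations, and neither stated scenario totals 60. The totals are 2 × 31 = 62 and 2 × 81 = 162.

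Remission is one of two primary measures and a chi-square test is a planned comparison, so what is at stake is how a non-significant remission result would be read. Under a true 80% power it would be fair evidence against the expected gain. Under 35–39% it would be very little.

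**Working it through.** **Inputs.** Two-sided alpha 0.05 (z = 1.960), power 0.80 (z = 0.842), control remission p0 of 50–60%, gain d of 20–30 points, and stated sizes of 81 and 31 per group, all from Design. Six blocks of 10, half per arm, from Randomization: 6 × 10 = 60, so 30 per arm.

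**Step 1: reproduce 81 and 31.** With p1 = p0 + d and p̄ the mean of the two rates, the pooled formula is

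n = [1.960·√(2p̄(1−p̄)) + 0.842·√(p0(1−p0) + p1(1−p1))]² / d²

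- 60% v 80%: [1.960·√0.42 + 0.842·√0.40]² / 0.04 = 81.2
- 60% v 90%: [1.960·√0.375 + 0.842·√0.33]² / 0.09 = 31.5

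These match the stated figures to within rounding; strict rounding up would give 82 and 32. The unpooled formula, n = (1.960 + 0.842)²·[p0(1−p0) + p1(1−p1)] / d², gives 80.9 and 30.1 at 58.4% control, which round up to exactly 81 and 31. So the sizes reproduce at about 58–60% control. A continuity-corrected formula at 60% gives 91 and 38. A one-sided calculation at 50% gives 74 and 31. Neither fits both figures.

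**Step 2: the rest of the cited range, pooled formula.**

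| Control | 20-point gain | 30-point gain |
|---|---|---|
| 50% | 93.0 → 93 | 38.5 → 39 |
| 55% | 88.1 → 89 | 35.4 → 36 |
| 60% | 81.2 → 82 | 31.5 → 32 |

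**Step 3: power of the stated sizes.** Exact power is the sum of the two binomial probabilities over all tables in which the uncorrected chi-square exceeds its 5% critical value.

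- 81 per group: 0.802 at 60% v 80%, but 0.739 at 50% v 70%.
- 31 per group: 0.813 at 60% v 90%, but 0.714 at 50% v 80%.
- At the 50% needs, power is 0.799 (93 per group, 20 points) and 0.813 (39 per group, 30 points).

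**Step 4: power of the 60 envelopes (30 per group), same exact method, no dropout.**

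| Control | 20 points | 25 points | 30 points |
|---|---|---|---|
| 50% | 0.351 | 0.516 | 0.692 |
| 55% | 0.363 | 0.545 | 0.737 |
| 60% | 0.392 | 0.595 | 0.796 |

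The chance of a non-significant result when the gain is real is one minus these values: 61–65% at 20 points, 40–48% at 25 and 20–31% at 30. The true gain needed for 80% power is 33.3, 31.8 and 30.1 points at 50%, 55% and 60% control, against an expected 20–30.

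**Step 5: precision at 30 per group.** The Wald 95% half-width with equal rates is 1.960·√(2p(1−p)/30): 25.3 points at 50% and 24.8 points at 60%.

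**The case against.** The strongest defence is that 81 and 31 are not errors. They reproduce at rates inside or at the edge of the cited range, and the section ties each to its own gain. That stands: the sizes are conditional figures whose condition is missing. A reader might also infer that the plan gives no control rate and no difference at all. It gives a range for both; what is missing is a commitment to one value.

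A reader might further infer that the trial is planned at 60 and undersized for both scenarios. The documents support neither half. Nowhere is 60 called the target or a cap, and the plan does not say whether more blocks could be made. The gap to 62 is one patient per arm and immaterial: at 60% v 90%, power is 79.6% with 30 per group and 81.3% with 31. In effect, 60 envelopes are the plan's own 30-point scenario at 60% control. Only the gap to 162 is large, and it bites only if a gain near 20 points is of interest. The plan's expected range does include that gain.

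It is also tempting to say that a non-significant result is likely across most of the expected range. Step 4 shows otherwise: it is more likely than not at 20 points, roughly even at 25, and a minority risk at 30.

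Finally, a pilot need not be powered for efficacy. That is true, but this plan quotes 80% power, names efficacy primaries and plans between-group tests, so the title alone does not tell the reader to discount the power statement.

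**Conclusion.** The point holds as a misstatement of power. The claimed 80% for 81 and 31 per group is correct only near 58–60% control remission. It falls to about 74% and 71% at the 50% end of the plan's own range. The only operational size, 30 per arm, delivers about 80% only near 60% v 90%; elsewhere in the range power runs from 35% up to the mid-70s. It should be fixed, because it affects how a primary result is read. The absence of a stated N or target difference, or of an explanation of the pilot label, would by itself be only missing detail.

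The n = 30 figures assume that 60 is the enrolled number, with 1:1 allocation, no dropout and an uncorrected chi-square. Fisher's exact test would give less: 26–30% at 20 points and 60–71% at 30. The control rate behind 81 and 31 is back-calculated, since the documents show neither rate nor formula. The figures cover remission only. Response is also primary, but no response rates are given, and the mixed-model analyses are outside this check.

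**What to change.** 1. In Design, state the control rate and formula actually used for 81 and 31. Do not simply write in 60%, which is an inference. Add the needs at 50% control: 93 and 39 per group by the pooled formula.
2. State the planned N and which difference it is meant to detect. If N is 60, replace the 80% power statement with: *With 30 per group, power for remission is 35–39% for a 20-point gain and 69–80% for a 30-point gain (control remission 50–60%, exact uncorrected chi-square, no dropout).*
3. Report the remission difference with its 95% CI (half-width about 25 points if the arms are equal) alongside the planned test. This adds to the chi-square comparison and does not replace it. Making the interval the sole basis for interpretation would be a matter of preference, not a correction.

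The cost is wording and one added interval, with no extra patients and no change to the design or the planned tests. The drawback is that the stated power becomes less favourable and the sponsor must commit to a number.

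### Read literally, the metal exclusion stops at chest and brain and omits skull, scalp and ear near the rTMS coil positions

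*Combined protocol and SAP*

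**What the plan says.** Metal is mentioned in one place, the Exclusion criteria under Study Population: "metallic objects in the chest or brain, cardiac pacemakers, and somatic diseases associated with brain dysfunction were excluded from the study". The same sentence also lists organic brain damage and a personal or family history of seizures. The remaining exclusions are "Pregnancy, use of coercive measures, severe suicidal risk, severe agitation or delirium, and alcohol or drug dependence (ICD-10) constituted additional exclusion criteria". The work-up that follows is described as "General physical and neurological examination will be supplied by routine blood tests and an electrocardiogram", with no metal or implant check named and no exclusion attached.

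The exposure is described elsewhere. The Introduction states: "An electromagnetic coil placed on the scalp produces an oscillating magnetic field that penetrates the scalp and skull unattenuated". The rTMS paragraphs, which follow Pharmacological Treatment, give two coil positions. For the first: "The motor threshold will be determined by placing the center of the coil on a line connecting the vertex with the auditory meatus". For the second: "The treatment site over the right dorsolateral prefrontal cortex is then found by moving the coil 5 cm anterior to this point".

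**The concern.** The protocol itself treats metal as a reason to exclude, and it does so even for the chest, which is farther from the coil than any part of the head. On its own account, scalp and skull are the first tissues the field crosses. Yet the criterion moves from chest to brain and leaves out what lies between the coil and the brain. No reason for that scope is given.

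What is at stake is the safety of an individual participant, and whether the eligibility rule screens for the exposure the protocol describes. A recruiting clinician who applied the text literally would turn away a patient with metal in the chest and accept one with a plate or fragment beneath the coil.

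**Working it through.** No arithmetic applies: the plan states no figure on this point and the conclusion needs none. The check sets the eligibility text against the exposure text.

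**Step 1. Where the coil is.** It rests on the scalp, first on the line between vertex and ear canal, then 5 cm forward of the motor point. That forward move ends over the right dorsolateral prefrontal cortex and the motor response is sought in the left hand, so both positions are on the right side. An ear lies at one end of the positioning line.

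**Step 2. What the field crosses.** Scalp and skull, without attenuation according to the Introduction, before it reaches cortex. The Introduction also calls the stimulation focal, and the coil is a figure-eight type, so the text does not imply equal exposure across the whole head.

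**Step 3. What the criterion covers.**

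| Site of metal or device | Named in the exclusion? | Relation to the coil, from the text |
|---|---|---|
| Chest; cardiac pacemaker | Yes | Away from the coil |
| Brain | Yes | Target organ |
| Skull or scalp near the two positions | No | In the tissue the field crosses |
| Ear at the end of the positioning line | No | Near the first position |
| Left side of the head, eye, teeth | No | Not established by the documents |

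Rows three and four are the gap.

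**Step 4. Whether other text closes it.** The other exclusions do not mention metal, implants or devices, and neither does the work-up. The only treatment guideline cited, under Electroconvulsive Therapy, concerns how ECT is given. Organic brain damage, or bodily illness that affects brain function, could remove some of these patients indirectly. A skull plate, scalp fragment or ear implant need not involve either.

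**Step 5. Which arm.** Motor-threshold finding is described before the sentence that divides patients into placebo and active trains, and nothing limits it to one arm. A threshold defined by a visible hand movement needs pulses that reach the cortex. Sham patients therefore appear to receive some active pulses. This is an inference; the protocol does not say so outright.

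**The case against.** The strongest reply is that the documents do not contradict themselves outright. They do not say what the field does to metal, so any account of specific harm, or of how grave it would be, comes from outside them. That stands, and no such account is relied on here. What remains is that the protocol already treats metal as disqualifying, and gives that rule a scope that does not follow its own description of the exposure.

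Three further objections also stand in part:

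- **Translation.** The text is an English version of a Danish original, and the word rendered as brain may have been broader. This cannot be tested here. It lowers confidence, but the English text is the submitted form and it says brain.
- **Overlap.** The brain-damage criterion may catch some of these patients, so it would be wrong to say that no other criterion could.
- **Unwritten practice.** Clinicians may well ask about metal anyway. Nothing in the documents says they do, and an eligibility rule should not depend on it.

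A reader might also infer that metal anywhere in the head lies directly in the field. The documents do not support this: stimulation is focal and right-sided, and unattenuated passage through scalp and skull says nothing about reach to the opposite ear or eye. Nor do they support a count of affected patients or a cap on candidates lost. They give no prevalence and no number screened, and a rule covering the whole head would, taken literally, also exclude ordinary dental metal.

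**Conclusion.** The point holds in limited form. As written in English, a patient with a metallic object or implanted device in the skull, scalp or ear near the two coil positions is eligible for rTMS unless another criterion happens to apply. The rule is stated, but its anatomical scope does not match the exposure described in the same document.

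The number of patients involved cannot be derived from the documents. No endpoint, sample-size figure or analysis is affected. The case for acting rests on participant safety and the small cost of correction.

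It assumes that the English wording is what was applied at screening, that no metal check was made outside the written criteria, and, for the sham arm, that threshold finding used active pulses in all patients.

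**What to change.** Reconcile the anatomical scope of the metal exclusion with the field described in the Introduction and the coil positions in the rTMS paragraphs, so that it also covers metal and implanted devices outside the brain but near the coil. The sponsor should set the exact boundary and state how dental metal is handled. The Danish original should be checked first: if its term is broader, correcting the translation may be enough. The item should then be confirmed and recorded at screening. If recruitment has ended, document how the criterion was applied.

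The cost is an eligibility wording change and one screening item. A few candidates may be lost; the documents give no figure for how many, and the number depends on where the boundary is drawn.

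### Response and remission are both primary with no rule for success, while the stated 5% level and 80% power belong to a single test of remission

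*Combined protocol and SAP*

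**What the plan says.** - **Endpoints.** Outcome measures: "Primary effect measures: percentage of response and remission". Response is a halving of the HAM-D total and remission is a HAM-D17 of 8 or lower. Neither definition is tied to a rating time.
- **Ratings.** The same section plans HAM-D at baseline, after the 3rd, 6th and 9th ECT, and again 4 weeks after treatment ends. None is called primary.
- **Sample size.** Design states that earlier research "has found remission rates on ECT between 50 and 60" percent and that "the difference in the incidence of remission was expected to be 20-30" percent. It gives 81 patients per group for a 20-point difference and 31 for a 30-point difference, with "80% power in a 2-sided test at a 5% significance level". No rate or effect is given for response.
- **Analysis.** Statistics: "Treatment and placebo groups will be compared based on a t-test or chi-square test dependent on which was most suitable". For two percentages that means, in effect, chi-square. The effect on HAM-D6, HAM-D17 and MDI over time "will be evaluated based on a last observation carried forward as well as quadratic linear mixed model". Carrying forward is stated for these scale scores, not for the two binary endpoints.
- **Timing.** Pharmacological Treatment runs the treatment period from baseline to the end of week 3. Electroconvulsive Therapy gives three treatments a week and nine on average.
- **Aim.** The Introduction asks to what degree "right prefrontal low frequency rTMS administered as add-on may accelerate the" antidepressant effect of ECT.

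**The concern.** A 5% level and 80% power have meaning only for a defined test. Here two endpoints are primary, one is used for the sample size, and nothing says how the two results combine into a conclusion. Three rules are compatible with the text: remission leads, either endpoint suffices, or both are required. Only the first keeps both figures in the Design section. The second raises the false-positive rate above 5%. The third keeps the error below 5% but changes the power.

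The rating time adds to this. With no primary rating named, the choice could in principle be made after the data are seen. What is at stake is whether a positive result could be read at the level the plan states.

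**Working it through.** **Step 1: reproduce the plan's sample size.** Pooled-variance formula for two proportions, two-sided 5%, 80% power, control remission 60% (top of the plan's range):

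n per group = [1.96·√(2p̄(1−p̄)) + 0.8416·√(p₁(1−p₁)+p₂(1−p₂))]² / (p₂−p₁)²

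- 60% against 80%: [1.96·√0.42 + 0.8416·√0.40]² / 0.04 = 81.2, rounded up to 82 (plan: 81).
- 60% against 90%: [1.96·√0.375 + 0.8416·√0.33]² / 0.09 = 31.5, rounded up to 32 (plan: 31).

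The plan's figures therefore come, to within one patient, from one two-sided 5% test of remission, with nothing allowed for a second primary endpoint.

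**Step 2: how strongly the two tests are correlated.** A HAM-D17 of 8 or lower is at least a 50% fall from any baseline of 16 or more, so remission is taken as nested in response. The and/or subscale entry criterion could admit a few lower baselines. With remission rate m and response rate p, the correlation is r = √[m(1−p) / (p(1−m))]. Remission of 50-60% comes from Design; response of 70-80% is an assumption, because the documents give none.

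**Step 3: normal approximation, no treatment effect.** Each test is significant if |z| > 1.96. P(both) = 0.05 + 0.05 − P(either).

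| m | p | r | either | both |
|---|---|---|---|---|
| 50% | 70% | 0.65 | 8.5% | 1.5% |
| 50% | 80% | 0.50 | 9.1% | 0.9% |
| 60% | 70% | 0.80 | 7.8% | 2.2% |
| 60% | 80% | 0.61 | 8.7% | 1.3% |

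**Step 4: exact check.** All outcomes were enumerated over three categories per arm (remission, response without remission, neither), using the uncorrected chi-square test. The group sizes are 30 ("Six blocks are created with 10 sealed opaque envelopes in each", so 60 envelopes, half per arm) and the plan's 31 and 81. Results follow the order of the table above.

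| per group | either | both | favouring rTMS, either |
|---|---|---|---|
| 30 | 8.6, 9.2, 7.6, 8.6% | 1.5, 0.9, 2.1, 1.2% | 4.3, 4.6, 3.8, 4.3% |
| 31 | 9.0, 9.6, 8.0, 8.9% | 1.6, 1.0, 2.3, 1.3% | 4.5, 4.8, 4.0, 4.4% |
| 81 | 8.5, 9.0, 7.6, 8.6% | 1.4, 0.9, 2.2, 1.2% | 4.2, 4.5, 3.8, 4.3% |

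Remission tested alone has an exact error of 5.2% (m = 50%) or 4.9% (m = 60%) at 30 per group, 5.6% or 5.2% at 31, and 4.9% or 4.8% at 81. Part of the higher figures at 31 per group is thus the discreteness of the chi-square test itself.

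**Step 5: power if both are required.** Joint power cannot exceed the power for remission alone, and it falls below it unless response succeeds whenever remission does. It cannot be computed, because no response rate or effect is given.

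**Step 6: the rating time.** Three weeks at three ECTs a week gives 3 × 3 = 9 treatments, so the end of the treatment period coincides with the rating planned after the 9th ECT. This is an inference; no section says it.

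**The case against.** The strongest reply is that the inflation is conditional. No section says that either endpoint suffices, and naming response and remission together can equally be read as requiring both. This stands: what is established is an undefined rule, not an inflated error rate. It does not rescue the plan, because under the both-required reading the Design section's power belongs to a different test.

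Second, the documents point to a lead endpoint and a time: only remission is sized, and week 3 ends the treatment period. This also stands in part, and makes the timing less open than the list of ratings suggests. But the acceleration aim makes the ratings after the 3rd and 6th ECT plausible candidates too, and nine ECTs is only an average.

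Third, the study is titled a pilot and attaches no decision to the result. That lowers the stakes, but the plan itself states a formal level and power.

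A reader might go further and infer that two endpoints at four post-baseline ratings make eight tests, with an error of 1 − 0.95⁸ = 33.7%. The documents do not support this. No section plans a primary test at every rating, and the figure assumes independence, whereas repeated HAM-D ratings on the same patients would be strongly correlated.

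**Conclusion.** The point holds as an undefined primary test and should be fixed, though it is not fatal to a pilot. The omission is certain from the text. Its size depends on the reading:

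- **Either endpoint suffices:** about 7.6-9.6% two-sided at one rating, of which 3.8-4.8% favours rTMS against a nominal 2.5%.
- **Both required:** about 0.9-2.3%, with power unknown.
- **Remission leads:** the nominal 5%, as sized.

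The first two ranges rest on remission of 50-60% from the plan, an assumed response rate of 70-80%, remission nested in response, and 30, 31 or 81 per group. A two-test error near 9.5% could also be obtained by assuming a correlation of only 0.3, but that would need a response rate of about 92-94%, which nothing in the plan suggests. The missing primary rating is a real but smaller gap, and no figure is put on it.

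**What to change.** In Outcome measures and Statistics, state the following:

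1. The single primary endpoint is remission (HAM-D17 of 8 or lower), compared by a two-sided chi-square test at 5%.
2. The primary rating is the end-of-treatment one, at the end of week 3 and planned after the 9th ECT. The rating at that time is used whatever number of ECTs the patient has had, which covers courses shorter or longer than nine.
3. Where that rating is missing, the last on-treatment HAM-D17 is carried forward, in line with the method already planned for the scale scores. Counting missing as non-remission is a sensitivity analysis only, since it could misclassify patients who stopped early after improving.
4. Response is secondary, tested at the same rating only if remission is significant.
5. The ratings after the 3rd and 6th ECT and at 4 weeks are secondary, reported with 95% confidence intervals.

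The cost is a short paragraph and no new rating. Response can no longer succeed on its own, and the acceleration aim rests on secondary estimates. If the investigators regard speed as the main question, they may prefer an earlier primary rating; what matters is that one is fixed in advance.

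The change adds no patients for multiplicity. Splitting alpha at 2.5% per endpoint would instead need 99 or 39 per group for remission (20 or 30 points, 60% control). Requiring both endpoints would also control the error, but needs a power calculation that the plan does not contain. That the plan gives 81 or 31 per group without choosing, while the envelopes provide 30, is a separate matter that this fix does not settle.
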